	
ventricular tachycardia, ventricular fibrillation, or torsade de pointes, or syncope due to an arrhythmia
 

3. Had a myocardial infarction within the 6 months prior to Screening

4. Has a known personal or family history or symptoms of long QT syndrome

5. Has any of the following ECG results at Screening (the ECG may be repeated once at Screening in consultation with the Medical Monitor):

a. If the subject is not on citalopram, escitalopram, or venlafaxine

i. QTcF >450 ms, if QRS duration <120 ms

ii. QTcF >470 ms, if QRS duration ≥120 ms

b. If the subject is on citalopram, escitalopram, or venlafaxine

i. QTcF >425 ms, if QRS duration <120 ms

ii. QTcF >450 ms, if QRS duration ≥120 ms

6. Has clinically significant laboratory abnormalities that, in the judgment of the Investigator or Medical Monitor, would jeopardize the safe participation of the subject in the study

7. Evidence of severe or medically significant hepatic or renal impairment on laboratory tests as assessed by the Investigator or Medical Monitor

8. Has uncontrolled diabetes or a glycosylated hemoglobin (HbA1c) >8% at Screening

9. Has laboratory evidence of hypothyroidism at Screening, as measured by thyroid-stimulating hormone (TSH) and reflex free thyroxine (T4). If TSH is abnormal and the reflex free T4 is normal, the subject may be enrolled

10. Has a body mass index (BMI) of <19 or >35

11. Has a known history of a positive hepatitis B virus (HBV), hepatitis C virus (HCV), or human immunodeficiency virus (HIV) test

12. Has a history of PD psychosis, schizophrenia, or other psychotic disorder, or bipolar I or II disorder. Subjects who are currently being treated for eating disorder, obsessive-compulsive disorder (OCD), attention deficit hyperactivity disorder (ADHD), panic disorder, acute stress disorder, or posttraumatic stress disorder (PTSD), according to DSM-5 criteria, are also not eligible.

--	---

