#### 4.3 Exclusion Criteria

1. Use of an antipsychotic within 3 weeks or 5 half-lives of Baseline (whichever is longer)
2. Has greater than New York Heart Association (NYHA) Class 2 congestive heart failure or Class 2 angina pectoris, sustained ventricular tachycardia, ventricular fibrillation, or torsade de pointes, or syncope due to an arrhythmia
3. Had a myocardial infarction within the 6 months prior to Screening
4. Has a known personal or family history or symptoms of long QT syndrome
5. Has any of the following ECG results at Screening (the ECG may be repeated once at Screening in consultation with the Medical Monitor):
  - a. If the subject is not on citalopram, escitalopram, or venlafaxine
    - i. QTcF >450 ms, if QRS duration <120 ms
    - ii. QTcF >470 ms, if QRS duration ≥120 ms
  - b. If the subject is on citalopram, escitalopram, or venlafaxine
    - i. QTcF >450 ms, if QRS duration <120 ms
    - ii. QTcF >450 ms, if QRS duration ≥120 ms
6. Has clinically significant laboratory abnormalities that, in the judgment of the Investigator or Medical Monitor, would jeopardize the safe participation of the subject in the study
7. Evidence of severe or medically significant hepatic or renal impairment on laboratory tests as assessed by the Investigator or Medical Monitor
8. Has uncontrolled diabetes or a glycosylated hemoglobin (HbA1c) >8% at Screening

9. Has laboratory evidence of hypothyroidism at Screening, as measured by thyroid-stimulating hormone (TSH) and reflex free thyroxine (T4). If TSH is abnormal and the reflex free T4 is normal, the subject may be enrolled
10. Has a body mass index (BMI) of <19 or >35
11. Has a known history of a positive hepatitis B virus (HBV), hepatitis C virus (HCV), or human immunodeficiency virus (HIV) test
12. Has a history of PD psychosis, schizophrenia, or other psychotic disorder, or bipolar I or II disorder. Subjects who are currently being treated for eating disorder, obsessive-compulsive disorder (OCD), attention deficit hyperactivity disorder (ADHD), panic disorder, acute stress disorder, or posttraumatic stress disorder (PTSD), according to DSM-5 criteria, are also not eligible.
13. Has a current diagnosis of delirium
14. Has a current primary diagnosis of borderline, antisocial, paranoid, schizoid, schizotypal, or histrionic personality disorder, according to DSM-5 criteria

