#### **4.5 Prior and Concomitant Therapy**

Lifetime antidepressant use and response is to be recorded. All other medications used within 24 weeks prior to Visit 2 through Visit 7 (telephone visit) or EOT are to be recorded.

In order to ensure that appropriate concomitant therapy is administered, it is [REDACTED] [REDACTED] consultation with the Investigator (unless the subject is receiving treatment for a medical emergency [REDACTED]) [REDACTED] ns

Prohibitions and restrictions for concomitant medications, as specified in [Appendix A](#) and [Appendix B](#), should be followed between Visit 1 (Screening) and Visit 6/EOT. Medications that can prolong QT interval are prohibited (or restricted if approved by the Medical Monitor or appropriate designee) as specified in Appendix A. These appendices do not constitute an exhaustive list and any questions regarding prohibited and restricted medications or the use of medications that could interfere with study conduct should be discussed with the Medical Monitor or appropriate designee.

If a subject is on a restricted or prohibited medication at Screening, the medication should be adjusted or discontinued only if it is determined by the Investigator to be clinically appropriate (e.g., if the subject's symptoms are not well-controlled or if the subject cannot tolerate the current medication).

The Investigator may prescribe, adjust, or discontinue appropriate medication to treat or manage AEs. If a prohibited medication is prescribed to treat an AE, the subject may remain in the study if the Sponsor and Investigator (or designee) determines that it is appropriate for the subject to remain in the study.

All other subjects who take a prohibited medication during the study will be discontinued, unless the discontinuation presents an unacceptable medical risk. The justification to allow a subject to continue in the study will be made by the Sponsor, with medical input from the Investigator, and will be documented. If a subject is allowed to remain in the study on prohibited medication that is not prescribed to treat an AE, this will be reported as a major protocol deviation and not a waiver.

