## 16 APPENDICES

### Appendix A Prohibited and Restricted Medications

Subjects taking prohibited medications at study entry will not be eligible for the study. Subjects taking prohibited medications during the trial will be discontinued, unless the discontinuation presents an unacceptable medical risk. The justification to allow the subject to continue in the trial will be made by the Sponsor/Medical Monitor with medical input from the Investigator, and will be documented. If allowed to remain in the trial, this will be reported as a major protocol deviation and not a waiver.

The table below lists prohibitions and restrictions by medication class, including representative medications within class. Medications within each class include but are not limited to the examples listed in this table. Any questions regarding prohibited and restricted medications should be discussed with the Medical Monitor or appropriate designee.

Medication Class	Medication a	Prohibition/restrictions
Antipsychotics other than pimavanserin	PROHIBITED 
 
All in class
 
	
 
Must be washed out 2 weeks or 5 half-lives (whichever is longer) prior to Baseline
 
All antipsychotics are prohibited
 

Anticholinergics	PROHIBITED 
 
Centrally acting anticholinergics                             
 
benztropine
 
biperiden
 
trihexiphenidyl
 
oral diphenhydramine
 
 
 
	
 
Centrally acting anticholinergic medications are prohibited and should be washed out and discontinued at least 2 weeks or 5 half-lives (whichever is longer) prior to Baseline
 

	UNRESTRICTED 
 
Peripherally acting anticholinergics
 
Topical diphenhydramine
 
	
 
Peripherally acting anticholinergic medications and topical diphenhydramine are allowed without restriction
 

Anticonvulsant and mood stabilizers	PROHIBITED 
 
carbamazepine
 
lamotrigine
 
lithium
 
phenytoin
 
	
 
Must be washed out prior to Baseline or for 5 half-lives of the drug
 
Prohibited throughout the study
 

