	RESTRICTED 
 
valproate
 
	
 
Valproate may be used if dose unchanged for at least 4 weeks prior to Baseline and dose should be expected to remain unchanged until the subject's final visit.
 

Antidepressants other than background therapy	PROHIBITED 
 
mirtazapine
 
nefazadone
 
fluvoxamine
 
	
 
Prohibited throughout the study
 
Must be discontinued at least 2 weeks or 5 half-lives (whichever is longer) prior to the Baseline visit
 

Medication Class	Medication a	Prohibition/restrictions
	
 
• mianserin
 
• trazodone
 
• amitriptyline
 
• nortriptyline
 
• imipramine
 
• trimipramine
 
• desipramine
 
• clomipramine
 
	
	
RESTRICTED
 
Restricted due to potential for QT prolongation are the following:
 
 
• citalopram
 
• escitalopram                             
 
• venlafaxine
 
 
 
	
 
• Current treatment with an antidepressant is not required. However, if the subject is taking one of the permitted antidepressants on the left, the dose must be unchanged for at least 4 weeks prior to Baseline and should be expected to remain unchanged until the subject's final visit
 
• Citalopram is restricted to a maximum dose of 20 mg/day. Escitalopram is restricted to a maximum dose of 10 mg/day. Venlafaxine is restricted to a maximum dose of 225 mg/day.
 
• Citalopram, escitalopram, and venlafaxine are prohibited in subjects with the following ECG results at Screening:                             
 
○ QTcF >425 ms, if QRS duration <120 ms
 
○ QTcF >450 ms, if QRS duration ≥120 ms
 
 
 

Medication Class	Medication a	Prohibition/restrictions
Anxiolytics	PROHIBITED 
 
• chlordiazepoxide
 
• diazepam
 
• flurazepam
 
	
 
• Prohibited at Baseline and throughout the study
 

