	
RESTRICTED
 
 
• arteminol/piperaquine
 
• azithromycin
 
• bedaquiline
 
• ciprofloxacin
 
• gemifloxacin
 
• norfloxacin
 
• ofloxacin
 
• quinine
 
• roxithromycin
 
	
 
• Ciprofloxacin and azithromycin are restricted
 
• Prohibited at Baseline but may be used during the course of the study to treat a bacterial infection (e.g., urinary tract infection, respiratory infection), post-Baseline at the discretion of the Principal Investigator (PI).
 
• Arteminol/piperaquine, bedaquiline, gemifloxacin, norfloxacin, ofloxacin, quinine, and roxithromycin are only allowed under the following conditions: 
 
○ The subject has a Baseline ECG with a QTcF <425 ms OR
 
○ The subject has a QTcF <450 ms at Baseline AND QRS duration ≥120 ms
 
 
 

Herbal and nutritional supplements	
PROHIBITED
 
 
• St. John’s wart
 
• S-adenosylmethionine (SAM-E)
 
• valerian root
 
• melatonin
 
• L-tryptophan
 
	
 
• Prohibited at Baseline and throughout the study
 

a Medications within each class include but are not limited to the examples listed in this table.

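### Section 4.3 sets the QTcF exclusion for subjects on citalopram, escitalopram or venlafaxine (QRS <120 ms) at >450 ms; the synopsis and Appendix A set it at >425 ms

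*Protocol*

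**What the plan says.** Exclusion 5 in Protocol Section 4.3 sets Screening QTcF limits by QRS duration and by whether the subject takes one of three QT-prolonging antidepressants. Item 5.b opens "If the subject is on citalopram, escitalopram, or venlafaxine", and its first line, 5.b.i, is "QTcF >450 ms, if QRS duration <120 ms". The same words appear under 5.a.i, which covers subjects not on these drugs.

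Two other places in the protocol give a lower limit for that group:

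- Synopsis, exclusion 5.b.i: "QTcF >425 ms, if QRS duration <120 ms".
- Appendix A, restricted antidepressants: "Citalopram, escitalopram, and venlafaxine are prohibited in subjects with the following ECG results at Screening", followed by >425 ms for QRS <120 ms and >450 ms for QRS of 120 ms or more.

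Section 4.5 says the Appendix A restrictions "should be followed between Visit 1 (Screening) and Visit 6/EOT". The introduction to Appendix A adds: "Subjects taking prohibited medications at study entry will not be eligible for the study". The SAP contains no ECG eligibility limits, so it does not settle the matter.

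**The concern.** The same subject can be eligible under one section and ineligible under two others. The looser number is in Section 4.3, the full list of exclusion criteria and the one a site is most likely to screen from; the synopsis presents its list as the main criteria. No statement says which text takes precedence.

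This is a cardiac safety criterion. Protocol Section 1.3 reports mean QTc prolongation on pimavanserin 34 mg, and the three antidepressants are restricted in Appendix A because they can prolong QT. A subject enrolled in error has been exposed to the combination at a QTcF the sponsor appears to have meant to exclude. Under Section 4.1 that subject must then be discontinued unless stopping is an unacceptable medical risk. If kept, the case is reported as a major deviation.

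**Working it through.** **Step 1. The limits side by side (Screening QTcF that excludes or prohibits).**

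| Group | QRS | Synopsis | Section 4.3 | Appendix A |
|---|---|---|---|---|
| Not on the three drugs (5.a.i) | <120 ms | >450 | >450 | – |
| Not on the three drugs (5.a.ii) | ≥120 ms | >470 | >470 | – |
| On one of the three drugs (5.b.i) | <120 ms | >425 | **>450** | >425 |
| On one of the three drugs (5.b.ii) | ≥120 ms | >450 | >450 | >450 |

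Only one cell disagrees. The gap is 450 − 425 = 25 ms.

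**Step 2. Which number was intended.** Three features point to 425:

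- With 450 in both lines of 5.b, the split by QRS has no effect. In 5.a the narrow-QRS limit is 470 − 450 = 20 ms below the wide-QRS limit. With 425, the corresponding difference in 5.b is 450 − 425 = 25 ms.
- With 450, 5.b.i repeats 5.a.i, so the drug-specific rule adds nothing when QRS is <120 ms. In the wide-QRS stratum it still adds 470 − 450 = 20 ms of strictness.
- Appendix A uses the same 425/450 division by QRS for certain restricted antimicrobials: "The subject has a Baseline ECG with a QTcF <425 ms", or below 450 ms with QRS of 120 ms or more.

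**Step 3. What 25 ms means on drug.** Protocol Section 1.3.1 gives an average prolongation of about 5 to 8 ms at 34 mg, and Section 1.3.2 gives a mean change of 9.4 ms at 12 weeks.

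- Entering at 450 ms: 450 + 5 = 455 to 450 + 9.4 = 459.4 ms on average, inside the >450 ms category in SAP Section 14.4.
- Entering at 425 ms: 425 + 5 = 430 to 425 + 9.4 = 434.4 ms, outside it.
- Entry value at which the mean shift reaches 450 ms: 450 − 9.4 = 440.6 to 450 − 5 = 445 ms. So only the top 5 to 9.4 ms of the 25 ms band crosses 450 ms on average.

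**Step 4. How many subjects could be in the band.** The documents give neither the number taking these drugs nor a QTcF distribution, so this step is assumption throughout. Suppose 4 to 12 of the 40 enrolled take one of the drugs, all have QRS <120 ms, every site applies Section 4.3 alone, and Screening QTcF is normal with mean *m* of 400 to 430 ms and SD *s* of 15 to 25 ms. Among those at or below 450 ms, the share above 425 ms is

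[Φ((450 − m)/s) − Φ((425 − m)/s)] / Φ((450 − m)/s)

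| m | s | Share |
|---|---|---|
| 400 | 15 | 0.047 |
| 410 | 20 | 0.209 |
| 420 | 20 | 0.358 |
| 430 | 15 | 0.593 |

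The extremes are 4 × 0.047 = 0.2 and 12 × 0.593 = 7.1 subjects.

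**The case against.** The strongest reply is that eligibility rules accumulate. A subject must clear Section 4.3 and also not be on a prohibited drug. Appendix A prohibits these drugs above 425 ms, applies from Screening and makes such subjects ineligible. Applying every text gives one answer, >425 ms, and Section 4.3 nowhere permits what Appendix A forbids. This stands, and it confines the problem to a site that works from Section 4.3 without the appendix. It does not make the number in Section 4.3 right, and nothing in the documents supports 450 as deliberate.

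The objections to size also largely stand. The subject count rests on assumed inputs. Its upper end needs about 63% of users to exceed 425 ms at Screening, since 1 − Φ((425 − 430)/15) = 0.63, and if sites follow the whole protocol the count is zero. The crossing of 450 ms is a weak measure of harm: subjects not on these drugs may also enter at 450 ms and would average the same 455 to 459 ms. The SAP's potentially clinically important limits are >500 ms and a change >60 ms, which these averages do not approach.

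There are other safeguards: dose caps on all three drugs in Appendix A, ECGs at Baseline, Week 2 and Week 8, an eligibility check at Baseline, the cardiac exclusions 2 to 4, and investigator or Medical Monitor judgment under exclusion 23. No separate Baseline QTcF cut-off is stated for these drugs, however, and none of these measures tells a site which Screening limit to use.

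**Conclusion.** The point holds. Section 4.3 item 5.b.i carries a limit 25 ms looser than the two other statements of the same rule, in one stratum: subjects on citalopram, escitalopram or venlafaxine with QRS <120 ms. That 425 ms was intended is an inference from the structure of the criteria and from Appendix A; it is strong, but the sponsor's medical team should confirm it. If 450 ms was meant, the synopsis and Appendix A are wrong instead, and a correction is needed either way.

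The practical exposure is small and cannot be sized from the documents; the 0.2 to 7 range shows only what the assumptions allow. The inconsistency itself does not depend on that range. The primary analysis, sample size and power are untouched. It should still be fixed, because it is a cardiac safety exclusion on which sites can reach opposite decisions about the same patient.

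**What to change.** Change Section 4.3 item 5.b.i from >450 ms to >425 ms, subject to medical confirmation, through a protocol clarification or administrative amendment, and send sites a notice.

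Check back as well. The synopsis reports that 9 subjects had already completed Week 8 at the interim review of the sample size assumptions, so dosing was under way. Identify every enrolled subject on one of the three drugs with QRS <120 ms and Screening QTcF above 425 and up to 450 ms, for safety review and deviation reporting. The deviation summary (SAP Section 7) and QTcF tables (SAP Section 14.4) already planned are enough; no new analysis is needed.

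A minor item for the same amendment: Appendix A says of antipsychotics "Must be washed out 2 weeks or 5 half-lives (whichever is longer) prior to Baseline", while exclusion 1 requires 3 weeks or 5 half-lives. That mismatch fails safe because exclusion 1 is the stricter text, but the two should agree.

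The cost is one corrected number, the optional washout alignment, a site notice, and at most a few more screen failures.

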#### **4.5 Prior and Concomitant Therapy**

Lifetime antidepressant use and response is to be recorded. All other medications used within 24 weeks prior to Visit 2 through Visit 7 (telephone visit) or EOT are to be recorded.

In order to ensure that appropriate concomitant therapy is administered, it is [REDACTED] [REDACTED] consultation with the Investigator (unless the subject is receiving treatment for a medical emergency [REDACTED]) [REDACTED] ns

Prohibitions and restrictions for concomitant medications, as specified in [Appendix A](#) and [Appendix B](#), should be followed between Visit 1 (Screening) and Visit 6/EOT. Medications that can prolong QT interval are prohibited (or restricted if approved by the Medical Monitor or appropriate designee) as specified in Appendix A. These appendices do not constitute an exhaustive list and any questions regarding prohibited and restricted medications or the use of medications that could interfere with study conduct should be discussed with the Medical Monitor or appropriate designee.

If a subject is on a restricted or prohibited medication at Screening, the medication should be adjusted or discontinued only if it is determined by the Investigator to be clinically appropriate (e.g., if the subject's symptoms are not well-controlled or if the subject cannot tolerate the current medication).

The Investigator may prescribe, adjust, or discontinue appropriate medication to treat or manage AEs. If a prohibited medication is prescribed to treat an AE, the subject may remain in the study if the Sponsor and Investigator (or designee) determines that it is appropriate for the subject to remain in the study.

All other subjects who take a prohibited medication during the study will be discontinued, unless the discontinuation presents an unacceptable medical risk. The justification to allow a subject to continue in the study will be made by the Sponsor, with medical input from the Investigator, and will be documented. If a subject is allowed to remain in the study on prohibited medication that is not prescribed to treat an AE, this will be reported as a major protocol deviation and not a waiver.

## **5 INVESTIGATIONAL PRODUCT**

### **5.1 Investigational Product Description**

The investigational product will be pimavanserin 34 mg (provided as two 17 mg NUPLAZID tablets). Tablets will be administered orally as a single dose once daily (QD).

#### **5.1.1 Formulation, Appearance, Packaging, and Labeling**

The Sponsor will supply pimavanserin (NUPLAZID) 17 mg tablets.

NUPLAZID tablets are intended for oral administration only. Each round, white to off-white, immediate-release, film-coated tablet is debossed with “P” on one side and “17” on the reverse. Each 17 mg NUPLAZID tablet contains 20 mg of pimavanserin tartrate, which is equivalent to 17 mg of pimavanserin free base. Inactive ingredients include [REDACTED]

[REDACTED] Additionally, the following inactive ingredients are present as components of the film coat: [REDACTED]

During the treatment period, study drug will be supplied in 60 count bottle(s) (NDC 63090-170-60). Bottle(s) will be distributed in a quantity sufficient to ensure the subject has an adequate supply of study drug between study visits.

#### **5.1.2 Product Storage and Stability**

Study drug Investigational product must be stored at 20°C to 25°C (68°F to 77°F); excursions permitted between 15°C and 30°C (59°F and 86°F) (see US Pharmacopeia [USP] Controlled

Room Temperature) in a secure area with restricted access and according to local and national regulations.

### **5.1.3 Dosing and Administration**

The first dose of study drug will be administered at the clinic; study drug will then be dispensed to the subject to take home. Each daily dose consists of 2 individual tablets that should be taken together. Subjects should be instructed to take 2 whole tablets, orally, once each day. Subjects should be instructed to not crush the tablets. The tablets may be taken with or without food.

### **5.1.4 Blinding**

This is an unblinded, open-label study. Subjects, site staff, and the sponsor will be aware that the subject is on a 34 mg dose of pimavanserin.

### **5.1.5 Study Drug Compliance**

If a subject misses 1 dose of study drug, he or she should not take an extra dose the next day.

### **5.1.6 Overdose**

An overdose is a deliberate or inadvertent administration of a treatment at a dose higher than the maximum recommended dose per protocol. It must be reported, irrespective of outcome, even if toxic effects were not observed ([Section 7.4.4](#)). All events of overdose are to be captured as protocol deviations.

## **5.2 Investigational Product Accountability Procedures**

The Investigator or designee will keep current and accurate records of the study drug product dispensed, used, and returned for each subject to assure the health authority and the Sponsor that the study drug is being handled appropriately. Subjects should be instructed to return all NUPLAZID bottles and unused tablets to the Investigator at regularly scheduled clinic visits and at the Week-8 (EOT) visit. [REDACTED]

[REDACTED]  
At the conclusion of the study, final study drug reconciliation will be conducted at the site. Final study drug accountability documentation will be maintained at both the site and at the Sponsor. Any remaining unused study drug and all used and unused packaging will be destroyed at the study site or returned to the Sponsor or its designee as per the applicable regulations. Documentation of study drug destruction will be recorded and maintained by both the Sponsor and the Sponsor's designee.

